6.2 Handling of Missing Data

No missing data will be imputed. Missing plasminogen activity or antigen data will be ignored in the calculation of PK parameters.

6.3 Analyses Plan

Details will be provided in a Statistical Analysis Plan (SAP), which will be finalized before the database lock.

6.3.1 Demographics and Baseline Characteristics

Subjects' demographic and baseline clinical characteristics will be summarized descriptively. Continuous variables will be presented as mean, standard deviation, median, and range. Categorical parameters will be presented as numbers and percentages.

6.3.2 Pharmacokinetic/Pharmacodynamic Analysis

The primary endpoint is the number and percentage of subjects who achieve the target plasminogen activity trough levels for at least 3 measurements in 12 weeks during Segment 2. Primary endpoint success is defined as at least 80% of evaluable subjects (i.e., 8 or more) achieving the target trough levels for at least 3 measurements in 12 weeks. The target trough level is defined as an increase in plasminogen activity level of at least an absolute 10% (10 U/dL) from the subject's individual baseline level. Baseline is defined as the plasminogen activity level measured before the first dose of IMP at Segment 1, Day -4 for subjects who undergo Segment 1 or at Segment 2, Day 0 for those who do directly enter Segment 2.

The secondary PK endpoints include individual PK profiles at the end of Segment 2, compared with their PK profiles at baseline, and trough plasminogen activity and antigen levels during Segment 2 and Segment 3.

Plasminogen activity and antigen levels will be presented by individual subjects and summarized descriptively (number of subjects, mean, standard deviation [SD], coefficient of variation [CV], median, minimum, maximum, geometric mean and associated CV). Individual and median profiles of the concentration-time data will be plotted using nominal times. Median profiles may be presented on both linear-linear and linear-log scales.

Standard PK parameters, including area under the curve (AUC), clearance (CL), mean residence time (MRT), volume of distribution (V_d) and terminal half-life ($t_{1/2}$) will be calculated using non-compartmental analysis and baseline-adjusted plasminogen activity levels derived from Segment

1 data and, if a subject is suspected to develop neutralizing antibody to the IMP, plasminogen activity levels at the end of Segment 2.

Additional PK compartmental analysis may be performed and best-fit model will be used for further individual PK prediction.

The summary statistics will include the number of subjects, mean, median, standard deviation, minimum, and maximum. The PK parameters will be summarized with the geometric mean and 95% confidence interval around the geometric mean

D-dimer is monitored as a potential pharmacodynamic marker to better understand if there is a relationship between the levels of D-dimer in subjects over time and the subject's potential response to therapy.

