
Statistical Methods
	
Analysis datasets
 
Safety population: Includes any subject who receives at least one dose of the IMP and provides safety data for at least one non-screening visit.
 
PK population: Includes any subject who has completed Segment 2 dosing and have provided sufficient samples for PK assessments.
 
Full Analysis Set (FAS): Includes any subject who receives at least 1 dose of the IMP and provided data for at least one post-baseline efficacy assessments.
 
Pharmacokinetic Analysis
 
The primary PK endpoint is the number and percentage of subjects who achieve the target plasminogen activity trough levels for at least 3 measurements in 12 weeks during Segment 2. The target trough level is defined as an increase in plasminogen activity level of at least an absolute 10% (10 U/dL) from the subject’s individual baseline level. Baseline is defined as the plasminogen activity level measured before the first dose of IMP at Segment 1, Day -4 for subjects who undergo Segment 1 or at Segment 2, Day 0 for those who do directly enter Segment 2. Primary endpoint success is defined as at least 80% of evaluable subjects (i.e., 8 or more) achieving the target trough levels for at least 3 measurements in 12 weeks.

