In the current study, an interim analysis was performed after the first 10 subjects completed 12 weeks of treatment with a data cutoff at 30 November 2016. All 10 of these subjects achieved target PK trough levels demonstrating the ability of Prometic's Plasminogen (Human) to serve as effective replacement therapy. Preliminary efficacy evaluation at 12 weeks revealed that 13 of 14 visible lesions had resolved, and the remaining lesion had improved from 15 × 5 mm at baseline to too small to be measured at 12 weeks. There were no recurrences and no new lesions during this period of observation. There were no deaths, serious adverse events (SAEs), or AEs resulting in discontinuation of study drug. The most frequent AEs were headache and nasopharyngitis. Nausea, diarrhea, rhinorrhea, sinusitis, epistaxis, back pain, pain in extremity, and hematuria were also frequent in adult subjects, and upper abdominal pain and cough were frequent AEs in pediatric subjects. A US Biologics Licensing Application was submitted based on these interim data; this application is under review. As of 14Dec2017 study enrollment is complete and all 15 enrolled subjects received at least 48 weeks of treatment. Three subjects in Norway completed the study as planned, with the remaining 12 subjects in the US continuing treatment until product licensing or study termination by the Sponsor. However, due to the delay in product approval, subjects at the US site will be allowed to enroll in Treatment Protocol 2002C018G and continue ongoing IMP treatment without any break in treatment. If subjects decide to enter Treatment Protocol 2002C018G, then they will return to the study site and complete the End of Study visit and sign an informed consent/assent for that study and stop participation in the current study. If subjects decide to not enter Treatment Protocol 2002C018G,

then they will stop IMP and return to the study site for a Safety Follow-up visit 30 days after the final IMP dose.

Subject dosing has been revised throughout the protocol from 6.0 mg/kg to 6.6 mg/kg of plasminogen to reflect the true concentration and dosing as agreed with FDA during the 05Oct2016 Pre-BLA Meeting (CRMTS# 10393).

Details of these studies can be found in the Investigator's Brochure (IB).

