3.3 Subject Population

A total of 15 subjects with hypoplasminogenemia will be enrolled in the study to ensure at least 10 evaluable subjects. At least 2 pediatric subjects (aged 2 to 18 years) will be enrolled.

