6.1 Datasets for Analysis

Safety population: Includes any subject who receives at least one dose of the IMP and provides safety data for at least one non-screening visit.

PK population: Includes subjects who have completed Segment 2 dosing and have provided sufficient samples for PK assessments.

Full Analysis Set (FAS): Includes any subject who receives at least 1 dose of the IMP and provided data for at least one post-baseline efficacy assessments.

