6.4 Sample Size

Approximately 15 subjects with hypoplasminogenemia will be enrolled in this study to achieve at least 10 evaluable subjects. No formal calculation was made for sample size because of the rarity of the disease. The sample size is based on known patients who have hypoplasminogenemia.

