6.5 Interim Analysis

The data in this study will be conducted in stages. An initial analysis of the PK data will be conducted when at least 10 subjects have completed Segment 2 dosing and have provided sufficient samples for PK assessments. The second data analysis will be conducted when all subjects have either completed the Week 48 visit or have withdrawn consent and completed the final safety visit. The final data analysis will occur when all subjects have completed the final safety visit or remain in the study in Segment 3 (US subjects only). Additional details for these analyses will be included in the Statistical Analysis Plan (SAP).

7 Management of Investigational Medicinal Product

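### The primary PK success rule treats 80% of evaluable subjects and 8 subjects as the same threshold, but from the planned minimum of 10 evaluable subjects upward they agree only at exactly 10

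*Protocol*

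**What the plan says.** Section 6.3.2 sets the criterion for the primary PK endpoint: "Primary endpoint success is defined as at least 80% of evaluable subjects (i.e., 8 or more) achieving the target trough levels". The Statistical Methods part of the Synopsis gives the same rule: "at least 80% of evaluable subjects (i.e., 8 or more) achieving the target trough levels for at least 3 measurements in 12 weeks".

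The denominator is not fixed at 10 anywhere:

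- Section 6.4: "Approximately 15 subjects with hypoplasminogenemia will be enrolled in this study to achieve at least 10 evaluable subjects". Section 3.3 also treats 10 as a minimum: "A total of 15 subjects with hypoplasminogenemia will be enrolled in the study to ensure at least 10 evaluable subjects". Section 3.6.3 allows replacement of withdrawn subjects to reach that same minimum.
- Section 3.1 counts as evaluable anyone who completes Segment 2 with three or more trough samples.
- Section 6.1 defines the PK population without a cap: "Includes subjects who have completed Segment 2 dosing and have provided sufficient samples for PK assessments".
- Section 6.5 sets even the first PK analysis by a minimum: "An initial analysis of the PK data will be conducted when at least 10 subjects have completed Segment 2 dosing".

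Section 1.3 reports the position when this version was written. On the interim analysis of the first 10 completers: "All 10 of these subjects achieved target PK trough levels". On the whole study: "As of 14Dec2017 study enrollment is complete and all 15 enrolled subjects received at least 48 weeks of treatment".

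**The concern.** The parenthesis is introduced as a restatement of the percentage, not as an example. A restatement as a fixed count needs a fixed denominator, and the protocol supplies only a lower bound. Up to 15 subjects may be evaluable; the exact number is not stated. For any number above 10, the count is the more lenient of the two forms.

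The trial is labelled pivotal and its sample size has no formal basis (Section 6.4), so this threshold alone decides whether the primary PK endpoint is met. If someone applied the count to more than 10 subjects, a proportion below 80% would be reported as success. Even if nobody did, two thresholds in the text leave the sponsor open to the suggestion that the easier one was chosen after the data were seen.

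**Working it through.** **Inputs.** Threshold 80%, restated as 8 (Synopsis; Section 6.3.2). Minimum evaluable n = 10 (Sections 3.1, 3.3, 3.6.3, 6.4). Enrolled and treated: 15 (Section 1.3). Interim result: 10 of 10 (Section 1.3). No true success rate is assumed in this section.

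**Step 1: reproduce the protocol's figure.** The smallest whole number of successes that reaches 80% is 0.80 × n, rounded up. At n = 10 this is 0.80 × 10 = 8, so the stated count is exact there.

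**Step 2: repeat for every n that the protocol and its enrolment allow.**

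| Evaluable n | 0.80 × n | Successes needed for 80% | 8 / n | Count falls short by |
|---|---|---|---|---|
| 10 | 8.0 | 8 | 80.0% | 0 |
| 11 | 8.8 | 9 | 72.7% | 1 |
| 12 | 9.6 | 10 | 66.7% | 2 |
| 13 | 10.4 | 11 | 61.5% | 3 |
| 14 | 11.2 | 12 | 57.1% | 4 |
| 15 | 12.0 | 12 | 53.3% | 4 |

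Within n ≥ 10 the two forms coincide only at n = 10.

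**Step 3: take the interim result into account.** Suppose the 10 interim successes keep that classification in any later analysis. The count of 8 is then already met at every n. The 80% rule still needs max(0, successes needed − 10) from the other n − 10 subjects.

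| Evaluable n | Other subjects | Still needed for 80% | Totals that pass the count but miss 80% |
|---|---|---|---|
| 10 | 0 | 0 | none |
| 11 | 1 | 0 | none |
| 12 | 2 | 0 | none |
| 13 | 3 | 1 | 10/13 (76.9%) |
| 14 | 4 | 2 | 10/14 (71.4%), 11/14 (78.6%) |
| 15 | 5 | 2 | 10/15 (66.7%), 11/15 (73.3%) |

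So five possible results remain on which the two forms would give opposite verdicts.

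**The case against.** The strongest reply is that the percentage plainly governs. It is the defining phrase, and the count is a gloss that is exact at the planned minimum. For any n ≥ 10, a result that reaches 80% necessarily includes at least 8 successes, so the gloss is true as a lower bound. Nothing in the protocol applies the count to more than 10 subjects. The one PK analysis reported had n = 10, where the forms agree, and Section 6.5 does not say that primary PK success is judged again on all completers.

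Disagreement is also now unlikely. It would need all 3 further subjects to fail at n = 13, at least 3 of 4 at n = 14, or at least 4 of 5 at n = 15. With an assumed uniform prior updated by 10 of 10, the predictive probabilities are:

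- n = 13: 6/(12 × 13 × 14) = 0.3%
- n = 14: (24 + 264)/(12 × 13 × 14 × 15) = 0.9%
- n = 15: (120 + 1,320)/(12 × 13 × 14 × 15 × 16) = 0.3%

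With an assumed fixed success rate of 80%, the n = 15 figure is 5 × 0.8 × 0.2⁴ + 0.2⁵ = 0.7%. Section 3.2 points the same way, since each subject's dosing interval is chosen by how long activity stays 10 percentage points above baseline. Finally, no alpha or hypothesis test is stated for this endpoint, so no error rate is affected, and the reported percentage would reveal any shortfall.

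Most of this stands, and it limits the weight of the point. It does not remove it. A lower bound is not the equivalence that the text asserts, and a count of 8 is not sufficient for 80% above n = 10. No section limits the count to a 10-subject analysis or ranks the two forms. Section 6.3.2 ties the rule to evaluable subjects in general, and Section 6.5 plans two further analyses without excluding this endpoint from them. Nor is this a detail left to the SAP: the protocol fixes the threshold itself, in two forms that an SAP could not both follow for 11 to 15 subjects.

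**Conclusion.** The rule is wrong as written. The stated count matches 80% only at 10 evaluable subjects; at 15 it is 4 subjects too low and corresponds to 53.3%. The harm is conditional. A result below 80% would pass only if the count were applied to more than 10 subjects, and the natural reading is that the percentage governs.

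Given 10 of 10 at the interim, and assuming those classifications stand, a conflict is confined to 13, 14 or 15 evaluable subjects and to totals of 10 or 11 successes that fall between 66.7% and 78.6%. That is improbable. The correction is still worth making, because the error sits in the success definition of a primary endpoint and appears twice. The number evaluable beyond the first 10, and their results, are not given in the protocol.

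**What to change.** In the Synopsis (Statistical Methods) and in Section 6.3.2, delete the parenthesis. Alternatively, reword the threshold along these lines: *at least 80% of the subjects evaluable at the analysis, rounded up to a whole subject (e.g., 8 of 10, 12 of 15)*. Either change makes the percentage govern at any number of evaluable subjects.

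The 80% threshold stays as it is, and no new data or analysis is needed. The cost is a wording change in two places, plus the listing, reasoning and submission that Section 10.4 requires for an amendment. As interim results are already known, the stated reason should say that the change corrects the arithmetic and leaves the threshold unaltered.

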- Prior to IMP infusion, blood samples for trough plasminogen activity, antigen, and D-dimer
- Vital signs (before and 15 minutes after infusion)
- IMP infusion (not administered if subject is discontinuing treatment)
- Blood samples for PK profile: plasminogen activity, antigen, and D-dimer (Section 3.5.2.6, not conducted if subject is discontinuing treatment)
- Concomitant medications
- AE assessments
- Review and collection of subject diary

3.5.1.9 Segment 3

The following assessments will be conducted at the study site every 12 weeks for 36 weeks in Norway or until the IMP licensing or study termination by the sponsor in the United States. During Segment 3, subjects will continue to receive the IMP at the same dosage and interval as Segment 2, with the possibility of modification based on discussion between the investigator and the sponsor. Subjects or their caregivers may administer the IMP at home if properly trained.

- Weight
- Vital signs
- Physical examination
- Urine pregnancy test (women of childbearing potential)
- Clinical assessments (Section 3.5.2.13), if indicated
 - Measurements and photographs of visible lesions
 - Imaging of non-visible lesions
 - Functionality testing
- Prior to IMP infusion, blood and urine samples for clinical laboratory tests (hematology, biochemistry, urinalysis, fibrinolysis panel, coagulation panel)
- Prior to IMP infusion, blood samples for virology (serology and PCR) testing
- Prior to IMP infusion, blood samples for anti-plasminogen antibody
- Prior to IMP infusion, blood samples for trough plasminogen activity, antigen, and D-dimer

- Vital signs (before and 15 minutes after infusion)
- IMP infusion
- Concomitant medications
- AE assessments
- Provision and review of subject's diary
- Clinical Global Impression (performed at the Week 48 Visit only)
- Quality of life assessment (performed at the Week 48 Visit only)

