Blood samples will be drawn and analyzed for plasminogen activity and plasminogen antigen levels at a Central Laboratory using validated assays. Plasminogen activity is assessed with a chromogenic assay developed and validated at a central specialty laboratory. Plasminogen antigen levels are determined by ELISA (Cell Sciences) and validated at a central specialty laboratory. For each sample taken for Plasminogen activity and antigen testing in Segments 1, 2, and 3 a backup sample will also be taken and stored at the Central Laboratory facility in case of repeat testing requirements. No backup sample is needed at the End of Study visit for subjects who decide to enter the treatment protocol.

Segment 1

Blood samples are drawn on Day -4 before the IMP infusion to establish baseline levels for plasminogen activity, antigen, and D-dimer and at the following time points after the end of the infusion: between 5 and 15 minutes, 6 hours (± 30 minutes), 24 hours (± 2 hours, Day -3), 48 hours (± 2 hours, Day -2), 72 hours (± 2 hours, Day -1), and 96 hours (± 2 hours, Day 0). An individual PK profile will be developed based on these time points.

Subjects who have had individual PK profile for 6 mg/kg Plasminogen with the sponsor, due to participation in the prior Phase 1 study, do not participate in Segment 1.

Segment 2

For subjects who do not undergo Segment 1, blood samples are drawn to measure plasminogen activity and antigen levels on Week 1, Day 0, before the first dose of the IMP is given, to establish the baseline levels.

For all subjects, blood samples will be drawn every 2 weeks before IMP infusion to measure trough levels through the final dose.

A full PK profile will also be done for all subjects at the end of Segment 2 (Week 12 visit) to evaluate the stability of individual PK profile after 12 weeks of IMP administration. As plasminogen is a consumable clotting factor, if significant lesion burden is present at the start of the study or if neutralizing antibody develops, a subject's PK profile may be altered by the end of the 12-week treatment period. At the Week 12 visit, blood samples are drawn before the IMP infusion and at the following time points after the end of the infusion: between 5 and 15 minutes, 6 hours (± 30 minutes), 24 hours (± 2 hours), 48 hours (± 2 hours), 72 hours (± 2 hours), and 96 hours (± 2 hours). The PK profile will be developed for each subject and compared with his or her prior PK profile(s).

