Furthermore, additional PK analyses may be performed at other time points during Segment 2 as needed, such as when a subject's trough level or antibody test suggests the appearance of neutralizing antibody against the IMP or when the dosing frequency has changed.

Segment 3

Blood samples will be drawn at each study visit every 3 months before IMP infusion to measure trough levels. Plasminogen activity and antigen, D-dimer spot levels will be measured at the End of Study visit for subjects who decide to enter Treatment Protocol 2002C018G.

PK Sample Handling:

Blood samples will be obtained, centrifuged, and resulting plasma will be transferred to, and frozen in a cryovial and stored at -20°C . All samples will be shipped frozen to a Central Laboratory for analysis. Details on processing and shipping of blood samples are provided in the Laboratory Manual.

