3.5.2.10 Antibodies to Plasminogen

A blood sample will be obtained, centrifuged, and resulting serum sample transferred to and frozen in a cryovial, stored at -20°C, and shipped frozen to a Central Laboratory for detection of anti-plasminogen antibodies. Testing for anti-plasminogen antibodies is performed by ELISA. If neutralizing antibodies are suspected based on the plasminogen activity levels, an assay for assessing binding versus non-binding antibodies will be implemented. Details on processing and shipping of blood samples are provided in the Laboratory manual. For each sample taken for Plasminogen antibody testing in Segments 1, 2, and 3 a backup sample will also be taken and stored at the Central Laboratory facility in case of repeat testing requirements. No backup sample is needed at the End of Study visit for subjects who decide to enter the treatment protocol.

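### Section 6.3.2 uses Week 12 data for AUC, CL and half-life only when neutralizing antibody is suspected, although the Week 12 profile is taken in all continuing subjects to judge PK stability

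*Protocol*

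**What the plan says.** **Parameter rule.** Section 6.3.2 and the Pharmacokinetic Analysis part of the synopsis name the data for the non-compartmental parameters: baseline-adjusted activity from Segment 1 and, "if a subject is suspected to develop neutralizing antibody to the IMP, plasminogen activity levels at the end of Segment 2". Compartmental modelling is optional.

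**Endpoint.** The same section states: "The secondary PK endpoints include individual PK profiles at the end of Segment 2, compared with their PK profiles at baseline". No antibody condition is attached.

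**Sampling and purpose.** Section 3.5.2.6 says: "A full PK profile will also be done for all subjects at the end of Segment 2 (Week 12 visit"). The samples are one before the infusion and six after it, to 96 h, and the stated purpose is to see whether individual PK stays stable over 12 weeks. Each subject's profile is to be set against the earlier one or ones. Section 3.5.1.8 makes the one exception: the profile is "not conducted if subject is discontinuing treatment".

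**Causes of change.** Section 3.5.2.6 names two: "if significant lesion burden is present at the start of the study or if neutralizing antibody develops, a subject's PK profile may be altered".

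**How suspicion arises.** Section 3.5.2.10 provides for a further antibody assay as follows: "If neutralizing antibodies are suspected based on the plasminogen activity levels". Section 3.5.2.6 allows extra PK work when a subject's "trough level or antibody test suggests the appearance of neutralizing antibody against the IMP".

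**The concern.** The protocol samples every continuing subject to answer a stability question, then confines the standard parameters that answer it to subjects with one of the two named causes of change.

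The subset is also not neutral. Suspicion can rest on activity levels, the same variable from which the parameters are calculated. Low activity would prompt it. If plasminogen is consumed more slowly as lesions clear (an inference; the protocol says only that PK may change), levels would rise, and rising levels give no reason to suspect antibody. A change tied to lesion burden would therefore tend to fall outside the rule. Section 1.3 reports 13 of 14 visible lesions resolved at 12 weeks in the first 10 subjects. It does not link this to clearance, but it shows that lesion burden did change over the period in question.

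At stake is the descriptive account of whether AUC, clearance and half-life shift under repeated dosing.

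**Working it through.** The protocol gives no figure to reproduce for this rule. The check is to follow the text through each type of subject, then to size the technical limits of the comparison.

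**Step 1. What the rule yields.** Subjects with a profile on file skip Segment 1, and footnote k of Table 2 says they need no initial profile in this study.

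| Subject | Segment 1 parameters | Week 12 parameters | Pair from this study |
|---|---|---|---|
| Did Segment 1, antibody suspected | yes | yes | yes |
| Did Segment 1, not suspected | yes | no | no |
| Skipped Segment 1, antibody suspected | no | yes | no (on-file profile only) |
| Skipped Segment 1, not suspected | no | no | no |

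Only the first row gives a within-study change. The last row gives no parameters from this study's data.

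**Step 2. How many subjects.** Section 1.3 states that all 15 enrolled subjects received at least 48 weeks of treatment. None of them stopped by Week 12, so up to 15 were due the profile. The protocol does not say how many skipped Segment 1 or had suspected antibody, so the row counts cannot be derived.

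**Step 3. What the remaining displays can show.** Levels and individual curves are presented for all, but they set a single-dose curve beside a repeat-dose curve. Take a one-compartment model with half-life t of 60 h (Section 1.1.2 gives about 2.5 days in healthy subjects) or 36 h (assumed), and dosing interval τ of 48, 72 or 96 h.

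- PK unchanged: ratio of Week 12 to single-dose increment = 1/(1 − 2^(−τ/t)).
  - t = 60 h: 2.35, 1.77, 1.49.
  - t = 36 h: 1.66, 1.33, 1.19.
- Clearance down 20% (assumed) at constant volume, t′ = t/0.8: ratio at the end of the interval = [2^(−τ/t′)/(1 − 2^(−τ/t′))]/2^(−τ/t).
  - t = 60 h: 3.12, 2.43, 2.12.
  - t = 36 h: 2.30, 1.97, 1.87.

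A higher Week 12 curve is thus expected even with stable PK, and reading a change from it requires the subject's own half-life. For one subject the two cases do separate: at 48 h dosing, 2.35 against 3.12 (t = 60 h) and 1.66 against 2.30 (t = 36 h).

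**Step 4. Can the parameters be had from the scheduled samples?** At approximate steady state, clearance is dose/AUC over one interval. The 48, 72 and 96 h samples fall at the ends of the three permitted intervals, so this AUC needs no extrapolation. The single-dose AUC does. The share beyond 96 h is 2^(−96/t):

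- t = 60 h: 2^(−1.6) = 0.33.
- t = 36 h: 2^(−2.67) = 0.16.

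**The case against.** Five arguments can be made against the point.

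1. **The endpoint is served.** It compares profiles, not AUC or CL. The protocol commits to that comparison for each subject, with level listings and individual plots. This stands. A reader might infer that a secondary endpoint has been left unanalysed; the text does not support that.

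2. **This is close to SAP territory, and the word only does not appear in the rule.** Section 6.3 leaves detail to the SAP, and nothing forbids further parameters. This stands in part. But the protocol does not stay silent: it states a condition, and no other sentence commits to Week 12 parameters for subjects outside it. A stated rule narrower than the stated purpose can be faulted without seeing the SAP.

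3. **Plots can separate accumulation from altered clearance.** A reader might infer that single-dose and repeat-dose curves cannot be told apart. That goes too far. The comparison is within subject, where the figures in Step 3 separate. In that model accumulation leaves the log-slope unchanged, whereas a clearance change at constant volume alters it. A pre-dose Week 12 sample also shows carry-over directly. What remains is that the slope and clearance which make the distinction are the quantities the rule leaves uncalculated at Week 12.

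4. **The fix is imprecise.** Up to a third of the single-dose AUC is extrapolated, and infusions may move by a day (footnote i of Table 2), so steady state is approximate. This stands as a limit. The extrapolated share is not itself the error, however: if that share were wrong by 20% (an assumption), the AUC would move by 0.16 × 0.2 = 3% to 0.33 × 0.2 = 7%.

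5. **The half-life range and the 20% fall are not trial data.** Correct. They illustrate; they do not estimate.

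**Conclusion.** The point holds in limited form. The parameter rule in Section 6.3.2 and the synopsis is narrower than the sampling, the purpose and the secondary endpoint in the same protocol. Applied literally, it gives paired parameters only to Segment 1 subjects with suspected antibody, a subset chosen partly on activity. It gives no parameters at all to subjects who skipped Segment 1 without suspicion.

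It affects one descriptive secondary PK endpoint. The primary PK and efficacy endpoints are untouched, no data are lost, and the parameters can still be calculated. Priority is low to moderate. The conclusion rests on the natural reading of the conditional clause, not on the illustrative half-lives.

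Two stronger readings are not supported. A reader might infer that no subject would have Week 12 parameters; that is possible if nobody is suspected, but the number cannot be derived. A reader might also infer a 10% bias in clearance comparisons, because the on-file profile is labelled 6 mg/kg in Section 3.5.2.6 and 6.6 mg/kg in the synopsis under Criteria of Evaluation (6.6/6.0 = 1.10). Section 1.3 describes that difference as a revision of the stated dose to reflect the true concentration. The labels need reconciling as a separate wording point, and they add no weight here.

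**What to change.** - Delete the antibody condition in the synopsis and Section 6.3.2.
- State that baseline-adjusted non-compartmental parameters will be calculated at Week 12 for every subject with an adequate Week 12 profile, with AUC and clearance taken over the dosing interval.
- Compare them descriptively within subject with the Segment 1 profile or, for subjects who skipped Segment 1, with the profile on file.
- Report antibody status and baseline lesion burden beside each subject's change, as descriptors and not as conditions for entry.
- Report the extrapolated share of each single-dose AUC. Leave adequacy criteria and other computational detail to the SAP, which Section 6.3 requires before database lock.
- Separately, reconcile the 6 and 6.6 mg/kg labels for the on-file profile with the explanation in Section 1.3, so that both profiles of a subject use one dose basis.

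The cost is a change of wording in two places and a few extra tables, with no new samples or visits. The drawback is the imprecision of the single-dose AUC beyond 96 h, about 16% to 33% of the total at the half-lives assumed above.
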